5.2.4 Electrocardiogram

5.2.4.1 12-lead resting ECG

Twelve-lead resting ECGs (I, II, III, aVR, aVL, aVF, V1 - V6) will be recorded using a computerised electrocardiograph (CardioSoft EKG System, GE Medical Systems, Freiburg, Germany) at the time points given in the [Flow Chart](#).

In order to achieve a stable heart rate at rest and to assure high quality recordings at comparable resting phases, all ECGs will be recorded for a 10-sec duration after the subjects have rested for at least 5 min in a supine position. The site personnel will be instructed to assure a relaxed and quiet environment so that all subjects are at complete rest during the recordings. ECG assessment will always precede all other study procedures of the same time point to avoid impact of sampling on the ECG quality.

Electrode placement will be performed according to the method of Wilson, Goldberger and Einthoven modified by Mason and Likar (hips and shoulders instead of ankles and wrists).

Proprietary confidential information © 2017 Boehringer Ingelheim International GmbH or one or more of its affiliated companies

Precise electrode placement will be marked with an indelible mark on the skin to allow reproducible placement throughout the study.

ECGs will be recorded as single ECGs or as triple ECGs (three single ECGs recorded within 180 sec) as indicated in the [Flow Chart](#). Three triple ECGs will be recorded at baseline as indicated in the [Flow Chart](#).

All locally printed ECGs will be evaluated by the Investigator or a designee.

ECGs may be repeated for quality reasons (like alternating current artefacts, muscle movements, electrode dislocation). For time points with triple ECGs, all three single ECGs will be repeated. For the repeats due to quality reasons, only the repeated ECG recordings will be sent to the central ECG lab, whereas the initially recorded ECGs will be discarded.

Additional (unscheduled) ECGs may be collected by the Investigator for safety reasons. These ECGs are assigned to the prior scheduled time point. Unscheduled ECGs will not be included into the statistical analysis of interval lengths.

For the inclusion or exclusion (see [Section 3.3](#)) of a subject and for the assessment of cardiac safety during the study, the QT and QTcB values generated by the ECG machines or their manual corrections by the investigators will be used. In doubtful cases, ECGs may be sent upfront for centralised evaluation (see below). In this case, these centrally measured results would overrule any other results obtained.

Abnormal findings will be reported as AEs (during the trial) or baseline conditions (at screening) if judged clinically relevant by the Investigator. Any ECG abnormalities will be monitored carefully and, if necessary, the subject will be removed from the trial and will receive the appropriate medical treatment.

A post-study centralised evaluation of the 12-lead ECGs recorded on Days 1 to 29 in Visit 3 will be performed by an independent ECG laboratory. This analysis will include the determination of cardiac axis as well as the intervals RR, PR, QRS and QT measured semi-automatically. Only the first of the three replicate ECGs at a single time point or at baseline will be evaluated. The remaining second and third replicate ECG will be stored for additional analysis if required, e.g. by authorities at a later time point.

For each QT interval, the RR interval preceding the QT will be measured to calculate the respective frequency corrected QTc intervals 'QTcF' according to Fridericia's formula ($QTcF = QT / RR^{1/3}$) and 'QTcB' according to Bazett's formula ($QTcB = QT / RR^{1/2}$). The QTcF correction will be used for evaluation and reporting. Abnormalities detected during centralised ECG evaluation will not necessarily qualify as AE. All interval measurements in one subject will be performed on the same lead. The intervals will be measured from four cardiac cycles (beats) in lead II. If lead II shows a flat T wave or is not measurable for any reason, lead V5 will be used, or if that lead is not measurable, then lead I will be used. The lead actually used will be reported in the CTR.

For blinding arrangements see [Section 4.1.6](#).

Assessed ECGs will comply with the ICH E14 guidance document and supplements [[R05-2311](#), [R13-0801](#), [R13-4095](#)] as well as the FDA requirements for annotated digital ECGs [[R09-4830](#)].

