3.3.3 Exclusion criteria

Subjects will not be allowed to participate if any of the following general criteria apply:

1. Any finding in the medical examination (including BP, PR or ECG) is deviating from normal and judged as clinically relevant by the investigator
2. Repeated measurement of systolic blood pressure outside the range of 90 to 140 mmHg, diastolic blood pressure outside the range of 50 to 90 mmHg, or pulse rate outside the range of 50 to 90 bpm
3. Any laboratory value outside the reference range that the investigator considers to be of clinical relevance
4. Any evidence of a concomitant disease judged as clinically relevant by the investigator
5. Gastrointestinal, hepatic, renal, respiratory, cardiovascular, metabolic, immunological or hormonal disorders
6. Cholecystectomy and/or surgery of the gastrointestinal tract that could interfere with the pharmacokinetics of the trial medication
 - except appendectomy and simple hernia repair
7. Diseases of the central nervous system (including but not limited to any kind of seizures or stroke), and other relevant neurological or psychiatric disorders
8. History of relevant orthostatic hypotension, fainting spells, or blackouts
9. Chronic or relevant acute infections
10. History of relevant allergy or hypersensitivity (including allergy to the investigational trial medication
11. Use of drugs within 30 days prior to administration of trial medication if that might reasonably influence the results of the trial (incl. QT/QTc interval prolongation)
12. Participation in another trial where an investigational drug has been administered within 60 days prior to planned administration of trial medication, or current participation in another trial involving administration of investigational drug
13. Smoker (more than 10 cigarettes or 3 cigars or 3 pipes per day)
14. Inability to refrain from smoking on specified trial days
15. Alcohol abuse (consumption of more than 30 g per day)
16. Drug abuse or positive drug screening
17. Blood donation of more than 100 mL within 30 days
 - intended donation during the trial

or
18. Intention to perform excessive physical activities within 4 days
 - or during the trial
19. Inability to comply with dietary regimen of trial site
20. A marked baseline prolongation of QT/QTc interval (such as QTc intervals that are repeatedly greater than 450 ms) or any other relevant ECG finding at screening

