3.3.4.2 Discontinuation of the trial by the sponsor

Boehringer Ingelheim reserves the right to discontinue the trial overall or at a particular trial site at any time for any of the following reasons:

1. New toxicological findings or serious adverse events invalidate the earlier positive benefit-risk-assessment. More specifically, the trial will be terminated if more than 50% of the subjects show drug-related and clinically relevant adverse events of moderate or severe intensity, or if at least one drug-related serious adverse event is reported.
2. The expected enrolment goals overall or at a particular trial site are not met
3. Violation of GCP, or the CTP, or the contract with BI by a trial site or investigator, disturbing the appropriate conduct of the trial
4. The sponsor decides to discontinue the further development of the investigational product.
5. Dose escalation will be stopped as soon as at least 2 subjects at one dose level on active drug showed relevant individual QT prolongation, i.e. a QTc increase of greater 60 ms from baseline in connection with absolute QT or QTc greater than 500 ms, which has been confirmed by a repeat ECG recording (e.g. follow-up ECG)
6. Dose escalation will be stopped based on preliminary PK results (plasma, see [Section 7.3.4](#)) as soon as measured (in at least one subject) or (upper limit of acceptable exposure in this trial, see [Section 2.1](#)). Further dose progression would be allowed only after a safety interim analysis and filing and approval of a pertinent protocol amendment.
7. Drug administration within a dose group and further dose escalation will be stopped if 3 or more of the subjects on active drug at the current dose level experienced vomiting of at least moderate intensity (see [Section 5.2.2.1](#) for definition of AE intensity)
8. Drug administration within a dose group and further dose escalation will be stopped if 2 or more of the subjects on active at one dose level experienced severe vomiting (see [Section 5.2.2.1](#) for definition of AE intensity)
- 9.

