6.6 HANDLING OF MISSING DATA AND OUTLIERS

Handling of missing data and outliers will be performed as described in the CTP, Section 7.4.

The only exception where imputation might be necessary for safety evaluation is AE dates. Missing or incomplete AE dates are imputed according to BI standards (see 001-MCG-156_RD-01 ([4](#))).

Missing data and outliers of PK data are handled according to BI standards (see 001-MCS-36-472_RD-01) ([5](#)).

If single cardiac cycles of an ECG (out of the generally four) are missing, the arithmetic mean for this single ECG will be computed with the reduced (1, 2 or 3) number of cardiac cycles.

If replicate ECG recordings are missing, the arithmetic means per time point will be computed with the reduced number (1 or 2) of recordings.

For the classification of the on-treatment QTc/QT intervals into “no new onset” / “new onset” categories, a missing value is obtained only in case that

- (i) all on-treatment values are missing and
- (ii) the baseline value is less than or equal to 500 msec, or missing.

If condition (i) is fulfilled but the baseline value is greater than 500 msec, this case will be categorized as ‘no new onset’. If baseline is missing and the maximum on treatment QTc interval is greater than 450 msec (or 500 msec for QT interval, respectively), this is classified as a ‘new onset’ in the respective category. If baseline is missing and the maximum QTc interval is less than or equal to 450 msec (or 500 msec for QT interval, respectively), this will be categorized as ‘no new onset’. If baseline is missing, a QTc/QT interval > 500 msec at any time on treatment will be a notable finding.

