7.8.4 ECG

12-lead ECG

Abnormal findings will be reported as baseline conditions (at screening) or as AEs (during the trial) if judged clinically relevant by the investigator.

All evaluations of ECG data will be based on the TS.

Listing of individual data

For all quantitative endpoints, listings of individual data will be shown in Appendix 16.2. For QTcB and RR only listings will be provided. Occurrences of notable findings will be flagged.

Comments regarding the ECGs will be listed.

Categorical endpoints

For the categorical endpoints, frequency tables will be provided.

For all subjects with any notable finding in ECG intervals, a separate listing will be created as end-of-text display (based on the same display template as in Appendix 16.2), and the corresponding time profiles will be shown.

Quantitative endpoints

Descriptive statistics (N, mean, SD, min, median, max) will be provided for the changes from baseline over time of QTcF, HR, QT, PR and QRS. The time profiles of mean and SD for the changes from baseline on treatment will be displayed graphically by treatment.

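### Does deciding on site QTcB but reporting QTcF hide whether the QT stopping rule was met?

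*Protocol*

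**What the plan says.** Criterion 5 stops dose escalation when at least two subjects on active drug at one dose level show "a QTc increase of greater 60 ms from baseline in connection with absolute QT or QTc greater than 500 ms", confirmed by a repeat recording. Criterion 20 excludes marked baseline prolongation, with "QTc intervals that are repeatedly greater than 450 ms" as its example. Neither names Bazett or Fridericia, and the protocol's abbreviation list allows either.

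Protocol 5.2.4.1 makes the assignment. For inclusion or exclusion, with a cross-reference to Section 3.3, and "for the assessment of cardiac safety during the study, the QT and QTcB values generated by the ECG machines or their manual corrections" apply. Doubtful recordings may go to the central laboratory: "In this case, these centrally measured results would overrule any other results obtained". For the post-study central evaluation, "The QTcF correction will be used for evaluation and reporting". That evaluation reads only the first replicate at each time point, and "Unscheduled ECGs will not be included into the statistical analysis of interval lengths".

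SAP 7.8.4 gives descriptive statistics for QTcF, HR, QT, PR and QRS. It then says: "For QTcB and RR only listings will be provided". The rules for missing values in SAP 6.6 again speak of QTc without a correction, for example "If baseline is missing and the maximum on treatment QTc interval is greater than 450 msec".

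**The concern.** Criterion 5 is the only numeric QT rule for stopping escalation in the visible text of a first-in-human trial. If the decision is taken on QTcB and the summaries show QTcF, the same recordings can satisfy the limits on one scale and not on the other whenever heart rate moves between baseline and the post-dose reading. A reader of the QTcF tables could then see no qualifying event where the site acted on one, or the reverse. The overruling clause adds a further doubt, because it does not say which correction the central value carries. What would be at stake is whether the report lets a reader trace an escalation decision to the data.

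**Working it through.** **Inputs.** The formulas are from Protocol 5.2.4.1: QTcB = QT/RR^(1/2) and QTcF = QT/RR^(1/3), with RR = 60/HR in seconds. The limits are from criterion 5: a rise above 60 ms, together with QT or QTc above 500 ms. The range of 50 to 90 bpm is the pulse range allowed at entry (exclusion criterion 2). The documents give no QT and heart-rate pairs, so those below are assumptions. The plan states no derived figure to reproduce.

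**Ratio of the scales.** Dividing the formulas gives QTcB/QTcF = RR^(-1/6) = (HR/60)^(1/6).

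| HR (bpm) | QTcB/QTcF | QTcF when QTcB = 450 | QTcF when QTcB = 500 |
|---|---|---|---|
| 50 | 0.970 | 463.9 | 515.4 |
| 60 | 1.000 | 450.0 | 500.0 |
| 70 | 1.026 | 438.6 | 487.3 |
| 90 | 1.070 | 420.6 | 467.3 |

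**Can one subject's result differ by scale?** Yes, in both directions.

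- *Heart rate rises.* QT 420 ms at 60 bpm, then 412 ms at 90 bpm. QTcB goes from 420.0 to 504.6 (+84.6, limits met). QTcF goes from 420.0 to 471.6 (+51.6, not met).
- *Heart rate falls.* QT 365 ms at 85 bpm, then 505 ms at 55 bpm. QTcB goes from 434.4 to 483.5 (+49.1, not met). QTcF goes from 409.9 to 490.6, a rise of 80.6 before rounding, with QT above 500 (met).

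**How far does this reach?**

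- The site scale cannot miss the 500 ms part when QTcF exceeds 500. At 60 bpm or below, QT is at least QTcF; above 60 bpm, QTcB exceeds QTcF. Only the 60 ms part can miss.
- A small slowing leaves almost no gap. From QTcF 430 at 70 bpm, QTcB is 430 × 1.026 = 441.2, so the QTcB rise passes 60 ms above 501.2. At 60 bpm the scales coincide, and they disagree only for a post-dose QTcF of 500 to about 501 ms.
- Heart rate alone does not trigger the rule at ordinary values. At a constant QTcF of 420, QTcB reaches 500 only at 60 × (500/420)^6 = about 171 bpm.

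The clear discordances therefore need heart-rate shifts of roughly 20 to 30 bpm and a post-dose QTcF of about 470 ms or more. Criterion 5 needs that in two subjects on active drug at one dose level, each confirmed. Recordings are made after at least 5 minutes of supine rest.

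**Can the report show it?** SAP 7.8.4 lists every quantitative ECG endpoint by subject, including QTcB and RR, and flags notable findings. It adds a separate end-of-text listing and time profiles for subjects with any notable interval finding. SAP Section 4 limits all analyses to the first two dose groups, planned as 2 × 6 = 12 active and 2 × 2 = 4 placebo subjects.

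**The case for a change.** The strongest case for a change is that the listings do not fully close the gap. The QTcB that Protocol 5.2.4.1 defines for the post-study evaluation comes from central, semi-automatic, first-replicate readings, whereas decisions rest on machine values or the investigator's corrections. A confirmatory repeat ECG, if unscheduled, stays outside the interval statistics. If a central QTcF were set against a site QTcB baseline (QTcF 430), the apparent change would shift by 430 × (1 − 1.070) = −30.1 ms for a baseline at 90 bpm, or 430 × (1 − 0.970) = +12.9 ms at 50 bpm (unrounded ratios used), which is large against a 60 ms limit.

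The first two facts stand, but the natural remedy does not answer them. A table of criterion-5 categories under both corrections would use the same central readings, so it still would not show the values on which the site acted. Those belong to the documented Safety Review before each escalation (Protocol 3.1), which includes ECG results and has signed, filed minutes. Protocol 7.3 also says that all individual data will be listed.

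The mixed-correction case supposes an error that the documents do not describe. The central laboratory's intervals yield both QTcB and QTcF, so a like-for-like comparison is available. The silence on which correction an overruling value carries is real, but it is a point of wording.

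The complaint about SAP 6.6 cannot be judged. The categories it refers to are not defined in the visible text, and parts of the SAP are not available.

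**Conclusion.** The concern does not call for a change. The arithmetic is right: the two corrections differ by 13.9 ms at 50 bpm and 29.4 ms at 90 bpm for a QTcB of 450, and by 15.4 and 32.7 ms for a QTcB of 500. One subject's qualifying event can therefore depend on the scale. But Protocol 5.2.4.1 says which scale serves decisions and which serves reporting, so the passages do not contradict each other. Repeating the correction beside criteria 5 and 20 would be tidier drafting and would alter no decision.

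The claim that the report cannot show whether the limits were met on QTcB goes too far. The summary tables do not show it, but the individual listings do for the central readings, and with 16 planned subjects in the two analysed groups they can be read directly. A further table would change no result or conclusion. An analyst may usefully note beside the QTcB listing that central first-replicate values can differ from the site and repeat values.

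This rests on assumed heart rates and QT values, and on the visible text only. The list of stopping criteria has a blank item, and some SAP sections cannot be seen.

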5.2.5 Assessment of other safety parameters

5.2.5.1 Vital signs

Systolic and diastolic blood pressures (BP) as well as pulse rate (PR) will be measured by a blood pressure device (Dinamap, GE Medical Systems, Freiburg, Germany) at the times indicated in the [Flow Chart](#), after subjects have rested for at least 5 min in a supine position. All recordings should be made using the same type of blood pressure recording instrument on the same arm if possible.

5.2.5.2 Medical examinations

At screening, the medical examination will include demographics including height and body weight, smoking and alcohol history, relevant medical history and concomitant therapy, review of inclusion and exclusion criteria, review of vital signs (BP, PR), 12-lead ECG, laboratory tests, and a physical examination. At the end of trial examination, it will include review of vital signs, 12-lead ECG, laboratory tests, and a physical examination with determination of weight.

5.3 OTHER

Not applicable.

5.4 APPROPRIATENESS OF MEASUREMENTS

All measurements performed during this trial are standard measurements and will be performed in order to monitor subjects' safety and to determine pharmacokinetic parameters in an appropriate way. The scheduled measurements will allow monitoring of changes in vital signs, standard laboratory values, and ECG parameters that might occur as a result of administration of trial medication. The safety assessments are standard, are accepted for evaluation of safety and tolerability of a subcutaneously administered drug, and are widely used in clinical trials. The pharmacokinetic parameters and measurements outlined in [Section 5.5](#) are generally used assessments of drug exposure.

5.5 DRUG CONCENTRATION MEASUREMENTS AND PHARMACOKINETICS

Date and clock time of drug administration and pharmacokinetic sampling will be recorded in the CRFs by the medical personnel. The actual sampling times will be used for determination of pharmacokinetic parameters.

PK sampling times and periods may be adapted during the trial based on information obtained during trial conduct (e.g. preliminary PK data) including addition of samples and visits as long as the total blood volume taken per subject does not exceed 500 mL. Such changes would be implemented via non-substantial CTP Amendments.

5.5.1 Pharmacokinetic endpoints

The following pharmacokinetic parameters will be determined for BI 473494 if feasible:

5.5.1.1 Secondary endpoints

- AUC_{0-tz} (area under the concentration-time curve of the analyte in plasma over the time interval from 0 to the last quantifiable data point)
- C_{max} (maximum measured concentration of the analyte in plasma)

5.5.2 Methods of sample collection

5.5.2.1 Plasma sampling for pharmacokinetic analysis of BI 473494

For quantification of BI 473494 plasma concentrations, 2.7 mL of blood will be taken from an antecubital or forearm vein into a K₃-EDTA (tripotassium ethylenediaminetetraacetic acid)-anticoagulant blood drawing tube at the times indicated in the [Flow Chart](#). Blood will be withdrawn by means of either an indwelling venous catheter or by veinpuncture with a metal needle.

The EDTA-anticoagulated blood samples will be centrifuged for about 10 min at about 2000 x g to 4000 x g and at 4 to 8 °C. Two plasma aliquots will be obtained and stored in polypropylene tubes. The first aliquot should contain at least 0.6 mL plasma. The second aliquot may contain 0.6 mL plasma or less. The process from blood collection until transfer of plasma aliquots into the freezer should be completed within 90 min with interim storage of blood samples and aliquots in an ice/water bath or on crushed ice. For each aliquot the time when the sample was placed in the freezer will be documented. Until transfer on dry ice to the analytical laboratory, the aliquots will be stored upright at about -20°C or below at the trial site. The second aliquot will be transferred to the analytical laboratory after the bioanalyst has acknowledged safe arrival of the first aliquot. At the analytical laboratory the plasma samples will be stored at about -20°C or below until analysis.

At a minimum, the sample tube labels should list the following information: BI trial number, subject number, visit, planned sampling time and “PK-1” or “PK-2”. Further information such as matrix and analyte may also be provided.

Plasma samples for PK analyses will be shipped to:

Boehringer Ingelheim Pharma GmbH & Co. KG
Drug Metabolism and Pharmacokinetics Germany
G144
[name]
[name], Germany

Proprietary confidential information © 2017 Boehringer Ingelheim International GmbH or one or more of its affiliated companies

After completion of the trial the plasma samples may be used for further methodological investigations, e.g. for stability testing, assessment of metabolites. However, only data related to the analyte and/or its metabolite(s) including anti-drug antibodies (if applicable) will be generated by these additional investigations. The study samples will be discarded after completion of the additional investigations but not later than 5 years upon the final study report has been signed.

